**Table 12. Schedule of assessments**

Assessments	Screening a	Safety Run-In (APR-548 Monotherapy) b										APR-548 + Azacitidine Combination												End of treatment x	Long-term follow-up y
												Cycle 1 (Safety Run-In)						Cycle 2				Cycles 3+			
		D1	D2	D3	D4	D5	D8	D15	D21	D28	D1	D2 - 7	D8	D15	D22	D1 c	D2 - 7	D8	D15	D1 d	D2 - 7	D15 e			
Informed consent	x																								
Mutant TP53 confirmation f	x																								
Medical history g	x																								
Physical examination h	x	x							x	x	x					x	x	x			x			x	
Vital signs h	x	x	x	x	x				x	x	x	x	x	x	x	x	x	x	x	x	x	x	x	x	
Height i	x																								
Weight	x	x							x	x	x					x	x	x			x			x	
ECOG performance status	x	x						x	x	x	x					x	x	x			x			x	
APR-548 j		x	x	x	x						x j	x				x j	x			x	x				
Azacitidine k											x	x				x	x			x	x				
Disease assessment l	x							x												x				x	
Hematology m	x	x					x		x	x	x		x	x	x	x	x	x	x	x	x	x	x	x	
Serum chemistry n	x	x					x		x	x	x		x	x	x	x	x	x	x	x	x	x	x	x	
Creatinine clearance o	x	x				x		x	x	x	x		x	x	x	x	x	x	x	x	x	x	x	x	
Coagulation profile p	x								x				x			x									
Pregnancy test q	x								x						x				x				x	x	
ECG r	x	x	x		x	x					x	x				x				x			x	x	
APR-548 PK sample s	x	x		x	x						x	x				x				x					
Azacitidine PK sample s											x	x													
PBMC/BMMC sample collection t	x					x													x			x			
Blood sample for PD markers u		x	x		x	x					x	x													
Bone marrow biopsy (optional)					x																				
Ophthalmological evaluation v	x						x		x				x	x				x	x	x	x v	x			
Clinical safety assessment w		Starting at the time of study treatment initiation through 30 days after last dose																							
Concomitant medications		Reviewed throughout study																							
Transfusion log		From 8 weeks prior to enrollment to end of treatment/off treatment																							
Survival																								x	

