4. Life-Threatening: Symptom(s) place the subject at immediate risk of death from the reaction as it occurred; it does not include a reaction that, had it occurred in a more serious form, might have caused death.
5. Fatal: Event caused the death of the subject.

AEs will be followed until resolution or stabilization while the subject remains on-study. Once the subject is removed from study, events thought to be related to the study medication will

be followed until resolution or stabilization, unless, in the investigator's opinion the event is unlikely to resolve due to the subject's underlying disease, or until the subject starts a new treatment regimen or the subject is lost to follow-up.

The end of the AE and SAE reporting period is 30 days after last dose of study treatment, unless the subject has withdrawn consent for study participation or started new therapy for underlying disease. Progression of primary disease should be reported on a response assessment eCRF in this FIH study. Events unequivocally related only to progression of primary disease do not need to be reported separately on the AE CRF page. Hospitalization to start new therapy for primary disease after confirmed progression/relapse does not meet reporting criteria for an AE or SAE.

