### **7.1.2.6 Reporting of Serious Adverse Events**

AEs classified as serious require expeditious handling and reporting to Sponsor's monitoring CRO to comply with regulatory requirements.

For any SAE that occurs while a subject is on-study; within 30 days of the last study treatment administration, regardless of any opinion as to the relationship of the SAE to the study treatment; or if any SAE that the investigator feels is related to the study treatment occurs later than 30 days after the last study treatment administration, [REDACTED] Safety Desk must be notified immediately (within 24 hours of becoming aware of the event). The primary mechanism for reporting an SAE to the sponsor will be the electronic data collection tool. An SAE eCRF should be completed in the electronic data capture (EDC) system within 24 hours of site becoming aware of the event. EDC Alerts will be sent to Safety desk for all SAEs.

If the EDC system is inaccessible/unavailable, then the site will use the paper SAE form in order to report the SAE within 24 hours. Emailing the paper SAE forms is the preferred method of notification.

SAEs will be reported to: Email: [REDACTED]

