## 8.3 Endpoints

### 8.3.1 Primary

1. Occurrence of DLTs, classified and graded according to the NCI-CTCAE version 5.0
2. Frequency of TEAEs and SAEs related to APR-548 alone and in combination with azacitidine
3. RP2D of APR-548

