## 8.5 Safety

Safety data including AEs, vital signs, laboratory data, ECG, ophthalmologic assessment findings, and other physical exam findings will be summarized for the safety population. AEs will be tabulated by system organ class (SOC), preferred term, severity, and relationship to treatments. The tabulation of laboratory parameters will include the normal ranges for each parameter. AE terms will be coded using the Medical Dictionary for Drug Regulatory Activities, version 22.1 or higher. AEs will be summarized by SOC, preferred term, severity, and relationship to treatment. SAEs, deaths, and AEs leading to APR-548 dose modifications including interruptions, reductions, and early discontinuation of study treatment will be summarized. Laboratory parameters will be summarized by maximum NCI-CTCAE version 5.0 severity grade and also by change from pre-treatment to scheduled time points using descriptive statistics. Laboratory parameter listings will include the normal ranges for each parameter. Each value will be classified as falling above, below, or within the normal range.

AEs are to be collected from the time of first dose of APR-548 and SAEs are to be collected from the time of signing informed consent, throughout study enrollment, and up to 30 days after last dose of APR-548 or azacitidine, whichever is later. Data summaries will include only TEAEs, defined as events occurring at the first administration of APR-548 up to and including 30 days after last dose of study treatment.

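### AE and SAE collection stops at new anti-MDS therapy in section 7.1.2.1 but runs to 30 days in sections 7.1.2.6, 8.5 and Table 12, and nothing says which rule governs

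*Combined protocol and SAP*

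**What the plan says.** Four places in the combined protocol and SAP set the end of safety collection.

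- **Section 7.1.2.1** gives a general end point, "The end of the AE and SAE reporting period is 30 days after last dose of study treatment", and then qualifies it: "unless the subject has withdrawn consent for study participation or started new therapy for underlying disease".
- **Section 7.1.2.6** requires 24-hour notification of any SAE that occurs on study or "within 30 days of the last study treatment administration, regardless of any opinion as to the relationship of the SAE to the study treatment". It also covers an SAE that the investigator considers related and that "occurs later than 30 days after the last study treatment administration". New therapy is not mentioned.
- **Section 8.5** collects events "up to 30 days after last dose of APR-548 or azacitidine, whichever is later" and defines TEAEs for the summaries as running "up to and including 30 days after last dose of study treatment". New therapy is not mentioned.
- **Table 12** gives the clinical safety assessment as "Starting at the time of study treatment initiation through 30 days after last dose". New therapy is not mentioned.

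The endpoint concerned is the second primary endpoint in section 8.3.1: "Frequency of TEAEs and SAEs related to APR-548 alone and in combination with azacitidine".

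**The concern.** The analysis window in section 8.5 is wider than the collection window in section 7.1.2.1 for any subject who starts other treatment for MDS within 30 days of the last dose. A site that follows 7.1.2.1 stops entering that subject's AEs on the day the new treatment starts. The section 8.5 tables still treat the subject as followed to Day 30, so a related event in the gap appears as no event. A site that follows 8.5 or Table 12 records the same event. With up to 10 centers and cohorts of 3 to 6 subjects, counts in a dose level could depend on which section a site read.

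For SAEs the difficulty is one of instruction: the same event is reportable under 7.1.2.6 and outside the reporting period under 7.1.2.1.

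The situation is foreseeable. Section 4.10.1 lists the start of new disease treatment as a reason to stop study treatment, and MDS in this population is expected to progress.

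**Working it through.** The plan states no figure to reproduce, so the check compares the texts and then works out the disputed time.

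**Step 1. One subject under each rule.** Let the last dose of study treatment be day 0, let new MDS therapy start on day d (d < 30), and let an event begin on day t.

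| Event | 7.1.2.1 | 7.1.2.6 | 8.5 | Table 12 |
|---|---|---|---|---|
| Non-serious, d < t ≤ 30 | Not collected | Does not apply (SAEs only) | Collected; counted as TEAE | Within the assessment period |
| Serious, d < t ≤ 30 | Not collected | Reportable whatever the relationship | Collected; counted as TEAE | Within the assessment period |
| Serious and related, t > 30 | Outside the period | Reportable, no end stated | Not collected; not a TEAE | Outside the period |

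The first row is the data gap. No other reporting section catches the event if the site follows 7.1.2.1. The second row is a conflict between two reporting instructions. The third row does not depend on new therapy, but it shows that SAE reporting has a further window that a reconciliation must also cover.

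The exception in 7.1.2.1 gives no alternative end date. The table takes the natural reading, that collection ends when the new therapy starts.

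**Step 2. Days in dispute for one subject.** Disputed days = 30 − d. The documents give no value of d, so these are assumptions:

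- d = 7: 30 − 7 = 23 days (23/30 = 77% of the window)
- d = 14: 30 − 14 = 16 days (16/30 = 53%)
- d = 21: 30 − 21 = 9 days (9/30 = 30%)

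**Step 3. What the schedule implies for d.** Planned azacitidine ends on Day 7 of a 28-day cycle. On-treatment disease assessments start at Cycle 3 Day 1 (±7 days; Table 12, footnote l). Counted from Cycle 2 Day 1, Cycle 3 Day 1 is Day 29, so the assessment falls 29 − 7 = 22 days after the last azacitidine dose, with a range of 15 to 29. If new therapy began on the day of that assessment, and Cycle 3 had not been started, the dispute would cover 30 − 22 = 8 days, with a range of 30 − 29 = 1 to 30 − 15 = 15 days. Footnote l also calls for assessment whenever progression is suspected, so earlier switches are possible.

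**Step 4. Effect on the endpoint.** The number of related TEAEs at risk is the sum, over subjects who start new therapy within 30 days, of their related events between day d and Day 30. That needs the proportion who switch, the distribution of d and the related-event rate. The documents give none of them, so the effect on event frequency cannot be computed.

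**The case against.** The strongest reply is that 7.1.2.1 defines the reporting period and 8.5 only summarizes it. The collection sentence in 8.5 can be read as an upper limit, with the exceptions left in 7.1.2.1. This is plausible for that sentence. It does not fit the TEAE definition in the same section, Table 12 or section 7.1.2.6, which each run to 30 days without qualification, and the document states no order of precedence.

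The exception may also be deliberate, to keep the next treatment's toxicity out of the APR-548 data. Copying it into the other three places would make the plan equally consistent. That stands: consistency is the requirement, and deleting the exception is a preference that needs its own reason (see the fix).

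Three stronger readings are tempting, and the documents do not support them.

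- A reader might infer that toxicity of the next therapy enters the primary endpoint wholesale under 8.5. Endpoint 2 counts related events, causality is assessed for each study medication (7.1.2.1), and 8.5 tabulates by relationship. Such events reach the all-cause tables, and the endpoint only if attributed to study treatment. Some could be, because the possible category in 7.1.2.2 admits events that other drugs could also explain.
- A reader might infer that SAEs after new therapy are lost. Section 7.1.2.6 captures them if the site follows it.
- A reader might infer that nothing is observed after new therapy starts. The visit about 28 days after the last dose (4.1.1, 6.8, Table 12) includes laboratory tests, ECG, an eye examination and a clinical safety assessment, with no exemption for subjects on new therapy. Part of the window is therefore seen, although under 7.1.2.1 the site need not record a new event.

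**Conclusion.** The inconsistency is in the current text and no redaction accounts for it. It should be corrected, but its weight is modest. The clear consequence is for non-serious related TEAEs between the start of new therapy and Day 30: one section stops their collection and another still counts the time. For SAEs the consequence is contradictory reporting instructions.

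Only subjects who start new therapy within 30 days of the last dose are affected, and the safety summaries are descriptive, with no hypothesis test. For one such subject the disputed time is 30 − d days: 1 to 15 days if the switch coincides with the Cycle 3 Day 1 assessment as in step 3, and up to 23 days under the assumed d = 7.

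A reader might go on to infer a percentage of the trial's safety follow-up that is lost. The documents give no switching rate or timing, and lost follow-up time is not the same as lost events, so no such figure is supported.

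Nor do the documents show that DLT assessment is cut short. Section 5.1.3 sets its own 28-day periods and does not tie them to the reporting period in 7.1.2.1.

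Whether transplant or its conditioning counts as new therapy is also not settled: section 4.10.1 lists new disease treatment and HSCT as separate reasons for stopping.

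**What to change.** Reconcile sections 7.1.2.1, 7.1.2.6, 8.5 and Table 12 to one window.

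1. Preferably, delete the new-therapy exception from 7.1.2.1, so that all AEs and SAEs are collected for 30 days after the last dose of APR-548 or azacitidine, whichever is later. Withdrawal of consent still ends collection. State that related SAEs after 30 days remain reportable under 7.1.2.6 and say how they are presented, since they fall outside the TEAE definition.
2. Record the start date of any new anti-MDS therapy or transplant conditioning. Sections 4.1.1 and 6.9 provide for collecting new antineoplastic therapies in follow-up but do not explicitly call for a start date.
3. In 8.5, tabulate TEAEs for the full 30 days and show those that begin after the recorded date separately.

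Deletion is preferable to copying the exception elsewhere because the separate tabulation lets either window be reported, whereas events that were never collected cannot be recovered. The cost is a few more AE entries and one date field, besides the wording changes.

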### **7.1.2.2 AE Relationship Attribution Definitions**

An AE is considered to be associated with the use of the study treatment if the attribution is determined as possible or definite.

The relationship of each AE to study treatment should be evaluated by the Investigator using the following criteria:

- Definitely related: A clinical event, including laboratory test abnormality, occurring in a plausible time relationship to the medication administration, and which cannot be explained by concurrent disease or other drugs or chemicals. The response to withdrawal of the drug should be clinically plausible.
- Possibly related: A clinical event, including laboratory test abnormality, with a reasonable time sequence to the medication administration, but which could also be explained by concurrent disease or other drugs or chemicals. Information on the drug withdrawal may be lacking or unclear.
- Unlikely related: A clinical event, including laboratory test abnormality, with little or no temporal relationship to medication administration, and which other drugs, chemicals, or underlying disease provide plausible explanations.
- Not related: A clinical event, including laboratory test abnormality that has no temporal relationship to the medication or has more likely alternative etiology.

### **7.1.2.3 Definition of an Unexpected Adverse Event**

An unexpected AE is defined as any adverse drug experience, the specificity or severity of which is not consistent with the reference safety information in the current Investigator's Brochure (IB) for a study product or products administered to a subject; or, if an IB is not available, the specificity or severity of which is not consistent with the risk information described in this protocol or in the regulatory agency study authorization application.

For study treatments used in this protocol that have been approved for use in the US by the FDA (i.e., azacitidine), the reference safety information that will be used for making expectedness decisions is the most current version of the product USPI that can be found on the FDA website.

Unexpected, as used in this definition, refers to an adverse drug experience that has not been previously observed (e.g., included in the IB or other product reference safety information such as the USPI) rather than from the perspective of such experience not being anticipated from the pharmacological properties of the pharmaceutical product.

#### **7.1.2.4 Serious Adverse Event**

An SAE is defined as any untoward medical occurrence that at any dose:

1. Results in death,
2. Is life-threatening (i.e., the subject was at risk of death at the time of the event. It does not refer to an event which hypothetically might have caused death if it was more severe),
3. Requires inpatient hospitalization or prolongation of existing hospitalization excluding that for pain management, disease staging/re-staging procedures, or catheter placement unless associated with other serious events,
4. Results in persistent or significant disability/incapacity, or
5. Is a congenital anomaly/birth defect.

Important medical events that may not result in death, be life-threatening, or require hospitalization may be considered serious adverse drug events when, based on appropriate medical judgment, they may jeopardize the subject and may require medical or surgical intervention to prevent one of the outcomes listed above.

#### **7.1.2.5 Pregnancy**

Any pregnancy detected during the study, or that occurs within 30 days after stopping study medication, must be reported immediately to the investigator. Pregnancy, in and of itself, is not regarded as an AE, unless there is suspicion that study medication may have interfered with the effectiveness of a contraceptive medication. If the subject becomes pregnant while on-study, the study drug should be immediately discontinued. Pregnancy information about a female subject or a female partner of a male subject should be reported immediately from the time the investigator first becomes aware of a pregnancy or its outcome. This will be performed by the investigator per instructions from the Sponsor's monitoring CRO.

Any pregnancy complication, spontaneous abortion, elective termination of a pregnancy for medical reasons, outcome of stillbirth, congenital anomaly/birth defect, or SAE in the mother will be recorded as an SAE and will be reported as described in Section [7.1.2.6](#).

### **7.1.2.6 Reporting of Serious Adverse Events**

AEs classified as serious require expeditious handling and reporting to Sponsor's monitoring CRO to comply with regulatory requirements.

For any SAE that occurs while a subject is on-study; within 30 days of the last study treatment administration, regardless of any opinion as to the relationship of the SAE to the study treatment; or if any SAE that the investigator feels is related to the study treatment occurs later than 30 days after the last study treatment administration, [REDACTED] Safety Desk must be notified immediately (within 24 hours of becoming aware of the event). The primary mechanism for reporting an SAE to the sponsor will be the electronic data collection tool. An SAE eCRF should be completed in the electronic data capture (EDC) system within 24 hours of site becoming aware of the event. EDC Alerts will be sent to Safety desk for all SAEs.

If the EDC system is inaccessible/unavailable, then the site will use the paper SAE form in order to report the SAE within 24 hours. Emailing the paper SAE forms is the preferred method of notification.

SAEs will be reported to: Email: [REDACTED]

### **7.1.2.7 Safety Monitoring Plan**

The Medical Monitor is responsible for ongoing safety monitoring for the study per the detailed safety plan. This monitoring will include a review of all SAEs as they are reported by the study site. The Medical Monitor will also be in contact with site monitors and will be available to discuss any issues concerning safety with site staff. Safety data will be reviewed periodically by [REDACTED] and the Sponsor Medical Officer.

DRT consisting of the Medical Monitor, Site Principal Investigators, independent retina specialist and other clinical research personnel that the Sponsor may deem appropriate, will hold DRMs on an interim basis at a frequency dependent on study accrual. At these meetings, the DRT will review AEs, DLTs and other safety data as applicable and make recommendations regarding dose escalation and the RP2D.

The DRT will produce summaries or minutes of these meetings. These summaries will be available for inspection when requested by any of the regulatory bodies charged with the safety of human subjects and the integrity of data.

## 7.2 Efficacy Assessments

### 7.2.1 Complete Remission Rate

CR rate will be summarized for the safety and efficacy-evaluable (EE) subjects as the proportion (%) of subjects with CR per the IWG 2006 criteria ([Appendix V](#)). In addition to presenting the CR rate, its associated exact 95% CI will also be presented.

### 7.2.2 Duration of Response

DOR is defined as the time from the date when criteria for response are met to the date of PD or death due to any cause, whichever occurs first. Subjects alive with no PD will have their DOR censored at the date of the last clinical assessment. The DOOR will be summarized by providing the median DOR together with associated 95% CI, using Kaplan-Meier methodology.

### 7.2.3 Overall Response

Overall response will be summarized in number (%) of subjects in each category of responses (CR, PR, marrow complete response [mCR] with HI, mCR without HI, HI). ORR will be analyzed by using the similar method as primary endpoint CR. DOR, as defined above, will also be evaluated in regard to ORR. Time to AML is calculated from first day of study treatment to first onset of AML. Kaplan-Meier methodology will be utilized. Rate of AML transformation will be analyzed by using the similar method as primary endpoint CR.

### 7.2.4 Overall Survival

Survival data are collected at treatment and follow-up periods. Subjects will be followed until death or withdrawal of consent from the study, whichever occurs first.

OS is defined as the number of days from the first day of treatment to the date of death due to any cause. Kaplan-Meier methodology will be utilized.

### 7.2.5 Relapse-Free Survival

RFS is defined as the time from the date of randomization to disease relapse or death, whichever occurs first. If neither event occurs, RFS will be censored at the date of the last clinical assessment. Kaplan-Meier methodology will be utilized.

